### **3. Short version of the project**

With the Medical Eye Trainer (MET) training system, patients suffering from dry age-related macular degeneration (AMD) are treated as part of the clinical routine. The MET system is an application (software) for a standard multimedia device such as a smartphone or tabletC.computer. The people affected by the disease treat themselves independently once a day for 90 seconds. The planned study will not introduce any new indications or therapies. Only data from ongoing therapies are collected, around to check the effect of the treatment. It turns around a Non-interventional study (NIS). It doesn't come to any study-specific risk increase, since there are no study-related interventions that go beyond the clinical routine.

## 4. Scientific background

### 4.1. General information

AMD is a disease of the eye that is widespread worldwide. According to the Gutenberg health study, around 7,000,000 people in Germany suffer from it. The figures for Austria can be assumed to be 700,000 due to the smaller population. A distinction is made between two forms of AMD, the wet form with 15% and the dry form with 85%. Both types have a high risk of developing significant visual impairment quickly. There are currently only a few therapeutic options for the dry form of the disease. Essentially, nutritional supplement therapy should be mentioned here. This treatment can only reduce the progression of deterioration in 10% of affected people, but it does have a significant side effect profile. This raises the question of completely different treatment approaches. Because of this, the Medical Eye Trainer (MET). This is a training device that can easily be used by yourself. The purpose of this new therapy is not to attempt to cure AMD. The eye and brain are trained to better deal with the disease. In a first study on 17 eyes, an improvement in visual performance could even be achieved in 11 cases, the remaining 6 cases showed a stable situation. In no case did it deteriorate. Thus it was possible for the first time not only to slow down this disease, but even to improve it. In a second study with a planned number of 150 examinations, this positive effect is to be investigated further. A calculation based on the results of the first study with G \* Power gives an optimal number of 150 examinations.

### 4.2. Risk-benefit assessment

The MET system is in clinical use. The patients are subjected to routine checks at the usual intervals. In the planned study there is only one data collection and evaluation. There is therefore no increase in risk. With this data evaluation, the effect of the therapy can be shown more precisely.

### **4.3. Examiner information**

The information collected corresponds to the usual clinical control of the participants.

Only one examiner is planned for the study, so no special information transfer is necessary.

## **5. Study objective**

### **5.1. aim**

The study aims to determine the therapeutic effect of MET im Check ongoing use on the patient.

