## **6. Subject recruitment**

### **6.1. Number of subjects and duration of the study**

According to the results of the first study, the calculation with the G \* Power system results in a number of 150 eyes. For the study, that number was doubled. The study is planned to last 6 months.

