### **6.2. Selection of subjects**

People who are already in therapy. can be taken into account in the data evaluation. In addition, the inclusion of additional test subjects is required. ArounddTo keep the recruitment phase short, general practitioners will be informed of the possibility of referring their patients to the study.

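### Sections 3, 4.2 and 5.1 speak of the effect of MET, but a one-group before/after comparison that may include existing users can show only the change in acuity during MET use

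*Combined protocol and SAP*

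**What the plan says.** All references are to the combined protocol and SAP.

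- **Aim.** Section 5.1: "The study aims to determine the therapeutic effect of MET". The rest of that sentence is damaged in translation, so the point does not rest on its verb. Section 3 gives the purpose as "Only data from ongoing therapies are collected, around to check the effect of the treatment", and section 4.2 says "With this data evaluation, the effect of the therapy can be shown more precisely". Section 4.1, after reporting the first study, adds that "this positive effect is to be investigated further".
- **Design.** Sections 3 and 5.2 describe a single-centre, non-interventional observational study. Section 9.1 repeats the initial examinations at a check after two months. Section 10.2 specifies a longitudinal comparison of the change. Section 10.5 lists three test names and nothing else. No section gives a comparator, masking, a repeat baseline, a natural-history reference or a limit on what may be concluded.
- **Examiner.** Section 4.3: "Only one examiner is planned for the study".
- **Natural course.** Section 4.1, on the wet and dry forms: "Both types have a high risk of developing significant visual impairment quickly".
- **Who is analysed.** Section 6.2: "People who are already in therapy. can be taken into account in the data evaluation". New participants are to be added. Section 7.2 records duration of illness and previous therapies, but names no date of first MET use.
- **Size.** Sections 6.1 and 10.3 give 150 eyes from G*Power, and then "For the study, that number was doubled", read here as 300 eyes. Section 4.1 speaks of 150 examinations.

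**The concern.** The stated target is an effect of MET. The planned quantity is a mean change from before to after in people who all use MET. That change is the sum of any MET effect and everything else that moves acuity over two months: familiarity with the test, expectation in the participant or examiner, and the course of the disease. The planned tests compare this sum with zero, so a significant result says that acuity changed, not why.

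The error can go either way. A small non-treatment gain could be reported as an effect of MET. Natural decline, which section 4.1 describes as a real prospect, could offset a true benefit and leave a null result.

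Admitting existing users adds a second difficulty. If such a person's baseline was taken after MET began, the change measured is between two points on treatment, not from before treatment to on treatment. Pooling it with the change in new users averages two different quantities. Without a MET start date, the planned data may not allow them to be separated.

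**Working it through.** **1. The plan's own figure.** The 150 eyes cannot be reproduced, because alpha, sidedness, power, effect size and SD are not given. A two-sided 0.05 paired t-test with a standardised change of 0.30 and 95% power needs 147 eyes, but those inputs were chosen to fit. What follows uses the planned numbers of eyes only.

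**2. Inputs.** From the documents: 150 or 300 eyes; paired before/after comparison; t-test. Assumed, because the documents give no values: letter scale; two-sided alpha 0.05; SD of change 5 / 7.5 / 10 letters; size of the non-treatment change; share of existing users. All results below are listed in that SD order.

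**3. Smallest significant mean change**, t(0.975, n−1) × SD / √n:
- n = 300: 1.968 × SD / 17.32 = 0.57 / 0.85 / 1.14 letters
- n = 150: 1.976 × SD / 12.25 = 0.81 / 1.21 / 1.61 letters

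**4. No MET effect, 1-letter non-treatment gain.** The chance of p < 0.05 comes from the noncentral t with n−1 degrees of freedom and noncentrality √n × 1 / SD.

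| Eyes | Noncentrality | Chance of significance |
|---|---|---|
| 300, independent | 3.46 / 2.31 / 1.73 | 93% / 63% / 41% |
| 300 acting as 200 | 2.83 / 1.89 / 1.41 | 80% / 47% / 29% |
| 150, independent | 2.45 / 1.63 / 1.22 | 68% / 37% / 23% |

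The middle row assumes that everyone contributes two eyes, a between-eye correlation of 0.5 and an analysis that allows for it: 300 / (1 + 0.5) = 200. The nominal rate is 5% throughout.

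**5. The other direction.** A 1.5-letter benefit with a 1-letter natural decline leaves a net 0.5 letter. With 300 independent eyes, power is 41% / 21% / 14%, so the result is non-significant in 59% / 79% / 86% of studies.

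**6. Pooling existing and new users.** Assume that half of 300 eyes belong to existing users who no longer change, and that new users change by 2 letters. The pooled mean is (0 + 2) / 2 = 1 letter, with SD √(SD² + 1).
- Pooled, 300 eyes: 92% / 63% / 40% by noncentral t (93% / 63% / 41% by simulation)
- New users alone, 150 eyes: >99% / 90% / 68%
- If instead all 300 eyes change by 2 letters: >99% / >99% / 93%

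So pooling dilutes the result if existing users have levelled off, and separating them costs power if they are still improving.

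**7. Limit on the argument.** Section 9.3 reports a 34% improvement in the first study. If that is decimal acuity (an assumption), log10(1.34) = 0.127 logMAR, and 0.127 / 0.02 is about 6.4 letters. A 1-letter shift would not explain a gain of that size.

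**The case against.** The best reply is that the study is openly observational, that its primary endpoint in section 5.3.1 is improvement in eyesight and not a difference attributable to MET, and that the aim is a badly translated sentence that may mean only checking MET in ongoing use. It can be added that every figure above except the number of eyes is assumed, that the one effect size in the documents is too large for a 1-letter artefact, and that natural decline works against a spurious gain.

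Much of this stands. A non-interventional study need not have a control group, and none is asked for here. The figures are illustration, not a forecast. But sections 3 and 4.2 carry the effect wording without the damaged sentence, and no section limits the conclusion.

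Some stronger readings are tempting but not supported:

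- **That the first study's gain was wrongly credited to MET (sections 4.1 and 9.3).** The documents do not give that study's design, so the absence of a comparator here says nothing about attribution there.
- **That existing users have a post-MET baseline.** No section says so. Section 4.2 mentions routine checks, so some may have a pre-MET acuity on file, and the previous-therapies item in section 7.2 may reveal earlier MET use. What is missing is a rule.
- **That the examiner reads the second acuity knowing the first.** The text is silent. A single examiner also limits between-examiner variation.
- **That a false claim will follow.** No section sets a reporting rule, so this is a risk and not a certainty.

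**Conclusion.** The point holds in a limited form. The plan aims at the effect of MET but can deliver only the change in acuity during MET use. It also admits existing users without requiring a pre-MET baseline, so the main result may mix two different changes. This should be settled before results are reported; the data remain usable.

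The mismatch between aim and design needs no assumption beyond the text. Its numerical size depends wholly on assumed inputs. Under those used here, a 1-letter non-treatment gain would be declared significant far more often than the nominal rate, and more often with 300 eyes than with 150. Allowing for correlated eyes reduces these chances but does not remove the problem. Neither the size nor the direction of any non-treatment change is known, and a gain of about 6 letters would need another explanation.

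**What to change.** 1. **Reword the aim.** Section 5.1: *The study describes the change in visual acuity between the examination before MET and the two-month check during MET use; without a comparison group this change is not attributed to MET.* Align section 3 (*to describe the change in visual acuity during MET use*) and the last sentence of section 4.2 (*The evaluation describes the change in visual acuity during MET use*). Leave the first-study statements in sections 4.1 and 9.3 as they are.
2. **Define the baseline.** Add the date of first MET use to section 7.2. State in sections 6.2 and 10.2 that the main before/after result uses eyes with an acuity value taken before MET started. A routine pre-MET record with a comparable two-month follow-up value counts. All other existing users go in a separate table.
3. **Describe the sample accordingly.** Say in sections 6.1 and 10.3 that the planned number of eyes covers both sets.

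**Cost.** Text changes in seven sections (3, 4.2, 5.1, 6.1, 6.2, 10.2 and 10.3), one data field in section 7.2 and one extra table; no added visits or staff. The headline claim becomes weaker. The main result has fewer eyes: if half of 300 lack a pre-MET value, 150 remain, and power falls if those left out are still improving. Section 11 requires the change to be reported to the ethics committee.

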### **5.2. Study design**

This observational study corresponds to a non-interventional study (NIS) and can therefore not be assigned to a normal phase of a study (I-IV).

The study is being carried out at a center.

### **5.3. Target parameters**

#### **5.3.1. Primary target point**

Eyesight improvement

#### **5.3.2. Secondary target point**

Improving the quality of life through better handling of the disease.

## **6. Subject recruitment**

### **6.1. Number of subjects and duration of the study**

According to the results of the first study, the calculation with the G \* Power system results in a number of 150 eyes. For the study, that number was doubled. The study is planned to last 6 months.

### **6.2. Selection of subjects**

People who are already in therapy. can be taken into account in the data evaluation. In addition, the inclusion of additional test subjects is required. ArounddTo keep the recruitment phase short, general practitioners will be informed of the possibility of referring their patients to the study.

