### **6.3. Inclusion criteria**

People with dry AMD are included regardless of age. Thus, this value is given as 20-99 years.

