### **6.4. Exclusion criteria**

Exclusion criteria are wet AMD, epilepsy and double vision. Other eye diseases are not a problemrepresent.

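### Sections 6.2 to 6.4 do not keep first-study eyes out of the evaluation, so eyes that suggested the effect could be counted again in the study meant to examine it further

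*Combined protocol and SAP*

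**What the plan says.** - **Who may enter.** Section 6.2 allows existing users: "People who are already in therapy. can be taken into account in the data evaluation". It adds: "In addition, the inclusion of additional test subjects is required". It gives no number or share for either group. Section 3 describes the source of data in the same spirit: "Only data from ongoing therapies are collected".
- **Criteria.** Section 6.3: "People with dry AMD are included regardless of age". It does not require eyes that have never used MET. Section 6.4: "Exclusion criteria are wet AMD, epilepsy and double vision". Earlier MET use and first-study participation are not listed.
- **The first study.** Section 4.1: "In a first study on 17 eyes, an improvement in visual performance could even be achieved in 11 cases", and "the remaining 6 cases showed a stable situation"; none became worse. Section 9.3 puts the improvement in eyesight at 34%.
- **Purpose of this study.** Section 4.1: "In a second study with a planned number of 150 examinations, this positive effect is to be investigated further". Sections 6.1 and 10.3 also derive 150 eyes from the first study's results, then double that number.
- **Analysis.** Section 10.2 plans a longitudinal comparison of change and describes no control group. Section 10.5 names the t test, Wilcoxon and Smirnov.

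**The concern.** A first-study participant who has dry AMD, is still training and has none of the three exclusions meets every written criterion. That person's eyes helped to produce the hypothesis and the sample size. If their old before/after values were pooled with the new data, the second result would no longer be independent of the first. The recounted eyes include improvements and no deteriorations, and without a control group nothing offsets them. The before/after test could then turn positive with no effect in any new eye.

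Inclusion of existing users is also optional, and no rule says which of them are taken. A choice made with knowledge of earlier results is therefore not ruled out.

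The gap is hard to repair later. Section 8.4 plans complete anonymization once data collection has ended. Section 7.1 records age as the only personal data, and section 7.2 asks about previous therapies but not first-study participation. Unless these eyes are marked at entry, an analysis without them may be impossible.

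**Working it through.** **1. The plan's own figure.** The 150 eyes cannot be reproduced, because alpha, sidedness, power, effect size, SD and the test entered in G*Power are not stated. If it came from a paired t test at two-sided 5%, 150 eyes would imply a standardised change d of about 0.23 (80% power), 0.27 (90%) or 0.30 (95%). This is used below only to bound the SD.

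**2. Share of the sample.** 17/300 = 5.7%; 17/150 = 11.3%. Both totals are shown because section 4.1 gives 150 examinations while 6.1 and 10.3 double 150.

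**3. Scenario.** All 17 eyes re-enter with their old values (11 better, 6 unchanged), and the other N − 17 eyes have no true change. The level is assumed to be two-sided 5%, so the nominal chance of a false improvement is 2.5%. Correlation between two eyes of one person is ignored.

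**4. Sign test.** The plan does not name this test. It is used because it needs only the 11/6/0 split and no SD. With no ties among new eyes, the untied eyes number (N − 17) + 11, and 11 improvements are already fixed.

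| | N = 300 | N = 150 |
|---|---|---|
| New eyes | 283 | 133 |
| Untied eyes | 294 | 144 |
| Improvements needed (upper tail ≤ 2.5%) | 165 | 85 |
| Needed from new eyes | 165 − 11 = 154 | 85 − 11 = 74 |
| False improvement, first-study eyes pooled | P(Bin(283, ½) ≥ 154) = 7.7% | P(Bin(133, ½) ≥ 74) = 11.2% |
| All N eyes new, for comparison | 2.2% | 2.0% |

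If 6/17 of new eyes are tied, the pooled figures are 10.1% and 16.0%; if half are tied, 11.7% and 18.8%.

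**5. t test.** Assume that 34% means log10(1.34) = 0.127 logMAR, as a mean over the 17 eyes. The fixed total is 17 × 0.127 = 2.159, spread equally over the 11 improved eyes (0.196 each). It moves the overall mean by 2.159/300 = 0.0072 or 2.159/150 = 0.0144. New eyes are drawn from N(0, SD²), with a one-sample t test at the upper 2.5% and 40,000 simulations per cell. The documents give no SD, so a range is used: 0.10 to 0.20 is a plain assumption, and 0.42 to 0.55 follows from step 1 (0.127/0.30 = 0.42; 0.127/0.23 = 0.55).

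| Assumed SD | N = 300 | N = 150 |
|---|---|---|
| 0.10 | 21% | 36% |
| 0.15 | 12% | 20% |
| 0.20 | 9% | 14% |
| 0.42 | 5% | 6% |
| 0.55 | 4% | 5% |

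Cross-check by normal approximation at N = 300, SD 0.20: shift = 2.159/(0.20 × √300) = 0.623; 1 − Φ((1.96 − 0.623)/√(283/300)) = 8.4%, close to the simulated 9%.

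If 0.127 applies only to each of the 11 improved eyes, the range is about 3.5 to 12% at 300 eyes and 4 to 20% at 150.

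**The case against.** The strongest reply is that the harm is hypothetical, and much of that reply stands.

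- **Planned reuse.** A reader might infer that the sponsor intends to recount the first-study eyes. No section says that any first-study participant is still training, is a candidate, or will have old values used. Section 3 limits the data to ongoing therapies, so eyes that stopped MET would not enter.
- **The described procedure points the other way.** Section 9.1 has participants examined, treated and re-examined after two months, and section 8.1 has all of them informed and consented for this study. Applied to an existing user, that yields a new before/after pair and recounts nothing. The harm arises only if old pre-MET values replace those examinations. Section 6.2 leaves room for this, because it does not say which values of existing users are used.
- **The examiner's knowledge.** It is tempting to say that the examiner already knows these eyes' results. Section 4.3 says only that this study has one examiner; who examined the first study's eyes is not stated.
- **A confirmatory trial.** The plan calls itself a non-interventional observational study and states no alpha or formal hypothesis. It says only that the effect is to be investigated further. Independence from the first study still matters for that aim.
- **The size.** The 36% needs the smallest assumed SD and the undoubled sample. It is a corner of the range and should not be quoted as the expected size.

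None of this closes the gap: the criteria as written admit these eyes, and no baseline or separate analysis is fixed for them.

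**Conclusion.** The point holds as an open gap in the selection rules. It is not evidence that data will be used twice. If all 17 eyes returned with their old values and new eyes had no effect, the false-improvement rate would exceed the nominal 2.5% under every assumption tried: modestly at 300 eyes with a large SD, severalfold with a small SD or at 150 eyes. The sign-test figures rest on the fewest assumptions. The t-test figures also depend on reading 34% as a logMAR gain and on an SD that the documents do not give. Fewer returning eyes, or new baselines for them, would reduce or remove the inflation.

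A reader might go further and conclude that every eye whose acuity under MET is already known should be excluded. The documents do not support that. Under the routine checks in section 4.2 it could remove most existing users and largely reverse section 6.2. The number of existing users is not given, so the cost cannot be sized, and nothing says that the doubled sample is a reserve for such losses.

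**What to change.** Add to sections 6.4 and 10.2: *Eyes that were in the first study do not enter the primary before/after comparison; they are flagged at entry, before anonymization, and may be listed separately.*

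For other existing users, keep them in as section 6.2 intends, and add a sensitivity analysis that reports their results separately from those of newly started eyes.

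The cost is one sentence, one entry field and one extra table. At most 17 eyes leave the primary comparison: 300 − 17 = 283 remain, or 150 − 17 = 133 if the target is 150, unless they are replaced.

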### **8.4. documentation**

The encrypted data can only be viewed and further processed by the examiner. It'll be a complete oneA.nanonymization of the original data is carried out after the data collection has ended. The study will be at<https://clinicaltrials.gov>registered and dealt with according to the specifications. These defaults are also used for the publication.

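### Section 6.2 sets no rule for which existing MET users enter the analysis, so inclusion can depend on a course already known; this can bias the mean gain upward if change is counted from before or early in MET use

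*Combined protocol and SAP*

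**What the plan says.** Section 6.2 (Selection of subjects) names two sources of participants. People already on MET "can be taken into account in the data evaluation". For new patients the wording is firmer: "In addition, the inclusion of additional test subjects is required", with general practitioners asked to refer. The split between the two sources is not given.

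Other sections bear on who could know what, and when:

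- Section 3: "Only data from ongoing therapies are collected".
- Section 4.2: "The patients are subjected to routine checks at the usual intervals".
- Section 4.3: "Only one examiner is planned for the study".
- Section 8.4: the data "can only be viewed and further processed by the examiner", and anonymisation follows only after data collection has ended.
- Section 6.3: "People with dry AMD are included regardless of age". This sets eligibility and has no criterion on when MET was started.
- Section 8.1: information and consent involve a supervising doctor. No selection rule is given.
- Section 9.1: examination, treatment with MET, and a repeat of the examinations after two months.
- Section 10.2: a comparison of change over time. No control group is described.
- Section 10.3: 150 eyes from G*Power, then doubled.

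No section gives a start-date window, a screening log, or a rule that inclusion be settled without sight of acuity results.

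**The concern.** In an uncontrolled before/after study the mean change is the whole result. If someone who knows how a patient has done can choose whether that patient counts, the choice can depend on the outcome. Even mild and unintended selection then moves the mean upward, and no comparison group offsets it. A larger sample does not help: the bias stays the same while the standard error shrinks, so doubling the eyes makes a false finding more likely.

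The existing users are the group for whom this is possible. A newly referred patient has no MET course to know about.

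**Working it through.** **No figure in the plan to reproduce.** The point concerns a missing rule. The 150 eyes cannot be rebuilt, because alpha, power, effect size and SD are not stated, and nothing below depends on how that number was reached.

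**Inputs.** From the plan: n = 150 or 300 eyes (section 10.3), and a one-sample comparison of change (section 10.2; the t test is among the methods in section 10.5). Assumed, because the plan does not give them:

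- true mean change of zero, normally distributed changes, eyes independent;
- f, the share of analysed eyes that come from existing users: 50% or 25%;
- d, the share of existing users with the least favourable course who are left out: 20%;
- ρ, the correlation between what is known at inclusion and the change finally counted: 1 (full knowledge) or 0.5;
- a two-sided 5% test, counting only significant results in the favourable direction (2.5% expected).

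**Step 1: shift among existing users.** Leaving out the lowest fraction d of a standard normal variable raises its mean by φ(z_d)/(1 − d), in SD of change:

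- d = 10%: 0.1755/0.9 = 0.195
- d = 20%: 0.280/0.8 = 0.350
- d = 50%: 0.399/0.5 = 0.798

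**Step 2: shift in the whole sample.** Shift = f × ρ × φ(z_d)/(1 − d). With d = 20%:

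- f = 0.5, ρ = 1: 0.5 × 1 × 0.350 = 0.175
- f = 0.5, ρ = 0.5: 0.5 × 0.5 × 0.350 = 0.0875
- f = 0.25, ρ = 0.5: 0.25 × 0.5 × 0.350 = 0.044

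**Step 3: chance of a false improvement.** A hand approximation is Φ(shift × √n − 1.96), with √150 = 12.25 and √300 = 17.32. A simulation of the t test gives the last column. It runs higher under full knowledge because cutting off the lower tail also shrinks the SD.

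| f | ρ | Shift (SD) | Hand, n = 150 / 300 | Simulated, n = 150 / 300 |
|---|---|---|---|---|
| 50% | 1 | 0.175 | Φ(0.18) = 57% / Φ(1.07) = 86% | about 64% / 91% |
| 50% | 0.5 | 0.0875 | Φ(−0.89) = 19% / Φ(−0.44) = 33% | about 20% / 34% |
| 25% | 0.5 | 0.044 | Φ(−1.42) = 8% / Φ(−1.20) = 11% | about 7% / 11% |

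With no selection (d = 0) the simulated rate was 2 to 3%.

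**Step 4: scale.** At two-sided 5% and 80% power, 300 eyes detect a standardised change of 0.16. A shift of 0.175 SD is as large as that; a shift of 0.044 SD is about a quarter of it (0.044/0.16 = 0.27).

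**Step 5: when ρ is above zero.** The calculation needs knowledge at inclusion that predicts the change later counted. If the counted change runs from before or early in MET use, part or all of it has been observed by then. If it runs from a new examination at study entry to the two-month check, it has not yet happened. The plan does not say which applies to existing users. Sections 3 and 6.2 speak of ongoing therapy and of evaluating data, which leaves room for the first reading. Section 9.1 can be read as the second.

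**The case against.** The strongest counter-argument is the baseline. If existing users follow section 9.1 from consent onward, with acuity measured at entry and again two months later, their change is unknown when they are chosen. Picking people with good past gains would then not act directly on the measured change. It could even pull it down, since a chance high reading at entry raises the past gain and lowers the next change. This stands, and makes the upward bias conditional.

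Other parts also stand:

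- A reader might infer that the single examiner decides who enters. The documents do not say so. Section 4.3 concerns passing on information, section 8.4 concerns access to data, and section 8.1 brings in a supervising doctor.
- Section 4.2 speaks of routine checks without naming acuity. That acuity is among them is an inference from section 9.1, which describes the usual AMD examinations.
- The sentence in section 6.2 is broken, and may mean only that existing users as a group are eligible too. Even so, no sampling rule is stated there or elsewhere.
- The bias would not be beyond repair. Comparing existing with new users would give a warning, and analysing new users alone would remove it.
- The shares and the correlation are assumed. Selection is of people while the count is of eyes; leaving out whole persons shifts the per-eye mean less unless the changes in both eyes are perfectly correlated.

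What does not stand is that section 6.3 closes the gap. It says who is eligible, not which eligible existing users must be approached.

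**Conclusion.** The point holds in a conditional form. The plan permits existing users to be counted without requiring all of them or a consecutive series, in an uncontrolled before/after design where their course may already be known. If their change is counted from before or early in MET use, the mean gain can be biased upward. With a fresh baseline at entry, selection on past gain would not act directly.

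A reader might go further and infer that favourable cases were chosen, or that the result is bound to be inflated. The documents support neither: they show only that nothing prevents it.

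The size is uncertain. With the worst 20% left out, the false-improvement rate runs from about 7% (150 eyes) or 11% (300 eyes) to about 64% or 91%, depending on the share of existing users and on how well their final change was known. All of these inputs are assumptions. The gap should be closed because closing it is cheap and the design has no other protection; confidence in the size is moderate at best.

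**What to change.** In section 6.2, replace the permissive sentence with an all-or-none rule, for example:

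> All persons who started MET at the centre between [date] and [date], including those who have since stopped, are listed by start date without reference to acuity. All who meet the criteria are invited, and all who consent are included. The numbers listed, invited, consenting and analysed are reported.

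Then:

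1. State in section 9.1 or 10.2 which examination is the baseline for existing users. Without this, the sampling rule leaves open what their change measures.
2. In section 10.5, make newly recruited participants with a baseline at entry the main comparison. At the least, report new and existing users separately.
3. If no complete list of MET starters can be made, report existing users descriptively only. The documents do not say whether records for such a list exist.
4. Bring section 3, which speaks only of ongoing therapies, into line with listing people who have stopped.

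Cost: a short amendment and one list. The downside is small: fewer eyes in the main comparison, or a less favourable mean gain once users with poor results are counted.
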